# 7.8 Dose Modifications – Interventional Component

#### 7.8.1 During the DLT assessment period

No dose modifications will be permitted in the first cycle of treatment. If a DLT is experienced, the trial medication considered to be related to the event must be promptly discontinued: 5-azacitidine must be suspended immediately, whereas the dose of ruxolitinib should be tapered by 5 mg decrements, to be completed over a 10-14 day period. The unrelated study drug may be continued at the discretion of the treating Investigator and the CI. If the DLT cannot be directly attributable to only one of the study drugs, both should be discontinued.

#### 7.8.2 Following completion of the DLT assessment period

Once the DLT assessment period has completed, patients may receive dose modifications on ruxolitinib and/or 5-azacitidine. Any change in dose should be recorded on the relevant CRF.

Dose reductions of ruxolitinib and/or 5-azacitidine are allowed in the event of unacceptable toxicity as per the SPC at the local investigator discretion.

Cycles of therapy may be delayed by up to 4 weeks in patients that experience toxicities. Cycle delays for reasons other than toxicities may be considered if clinically indicated and must be discussed and agreed previously with the CI via the Trials Office. If a patient experiences a delay of a new cycle for more than 4 weeks or experiences 3 successive cycle delays, treatment with ruxolitinib and/or 5-azacitidine will be permanently discontinued.

After completion of the first cycle, ruxolitinib dose escalations are allowed in the event of inadequate efficacy. For patients receiving ruxolitinib alone (e.g. following azacitidine interruption due to unacceptable toxicity), dose escalations will be conducted as per SPC at the discretion of the treating Investigator.

For patients receiving combination therapy, ruxolitinib dose escalations are allowed in the event of inadequate efficacy in the absence of unacceptable toxicities after completion of 3 cycles of treatment. The dose limit for ruxolitinib will be set at the highest dose level which previously received a positive assessment from the TSC (highest dose level with reported DLT rate not exceeding the target toxicity rate of 25%). Dose increments should also follow SPC guidelines prior to these limits being reached.

Once the MTD is declared, patients recruited at a lower dose may receive the MTD for any subsequent cycles of treatment at the discretion of the treating Investigator and the Chief Investigator.

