#### Renal toxicities

The kidney plays a significant role in the excretion of 5-azacitidine and ruxolitinib and the effects on renal function should be carefully monitored before the start of each cycle according to local protocols. If eGFR falls to between 30-39ml/min whilst the patient is receiving treatment with azacitidine,

bicarbonate levels should be measured at the time of serum biochemistry and patient should receive dose reductions according to SPC as applicable.

In the event of worsening kidney function (eGFR<30ml/min, grade 3 chronic kidney disease), the current azacitidine cycle should be interrupted and the next cycle delayed until the eGFR resolves to  $\geq$ 30ml/min.

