# 7.12 Patient Follow Up

#### Interventional Component

Patients who are gaining clinical benefit at the end of 6 cycles may continue to receive therapy with 5azacitidine and/or ruxolitinib at the discretion of the CI until loss of response or unacceptable toxicity. Patients that have to discontinue the combination therapy due to a toxicity that is clearly related to just one of the trial treatments may continue to take the alternative medication as long as they continue to obtain a clinical benefit in the view of the local investigator and the Chief Investigator (section 7.8.1). Patients will be followed-up for survival data for a minimum of 1 year from the date of start of treatment.

All patients must have a final assessment 28 days after the last dose of trial medication.

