# 7.13 Treatment Discontinuation and Patient Withdrawal

In the event of discontinuation of study treatment, e.g. unacceptable toxicity or patient choice, full details of the reason/s for discontinuation should be recorded on the CRF.

All patients, including non-compliant subjects, should be followed up according to the protocol unless they withdraw specific consent.

In the event of a patient's decision to withdraw from the trial, the Investigator should ascertain from which aspects of the trial the patient wishes to withdraw and record the details on the appropriate CRF. All information and blood/tissue samples collected up until the point of retraction will be retained and analysed. If a patient chooses to withdraw from treatment only (interventional arm only), the patient should discontinue treatment and continue to be assessed in accordance with the protocol. If a patient wishes to withdraw from the trial (i.e. including trial specific assessments), but is willing for further data to be supplied to the Trials Office, then further routine 'follow-up' data (e.g. toxicity data) will continue to be supplied by the Investigator to the Trials Office.

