#### Interventional Component

Patients who stop treatment due to adverse experiences (clinical or laboratory) will be treated and followed according to accepted medical practice. All pertinent information concerning the outcome of such treatment must be recorded in the CRF.

The following are justifiable reasons for the Investigator to stop study treatment:

- Unforeseen events: any event which in the judgement of the Investigator makes further treatment inadvisable
- Serious violation of the trial protocol (including persistent patient non-attendance and persistent non-compliance)
- Stopping by the Investigator for clinical reasons not related to the study drug treatment

Patients must stop study treatment in the event of:

- Occurrence of a DLT
- Unacceptable toxicity
- SAE requiring permanent discontinuation of treatment
- Occurrence of pregnancy in female participant

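### After cycle 1, section 7.8.2 allows dose reduction for unacceptable toxicity, but section 7.13 makes the same undefined term a mandatory reason to stop study treatment

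*Protocol*

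**What the plan says.** Three sections of the protocol give instructions for the interventional component that turn on this term or on the same situation.

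- **Section 7.8.2**, which applies after the DLT assessment period: "Dose reductions of ruxolitinib and/or 5-azacitidine are allowed in the event of unacceptable toxicity as per the SPC", with the decision left to the local investigator. Later in the section, ruxolitinib given alone is discussed, and azacitidine interruption for unacceptable toxicity is the example of how a patient gets there.
- **Section 7.13**, interventional part: a list headed "Patients must stop study treatment in the event of" has four entries: a DLT, "Unacceptable toxicity", an SAE that calls for permanent discontinuation, and pregnancy. The general opening of 7.13 also uses the term as an example of why treatment ends: "In the event of discontinuation of study treatment, e.g. unacceptable toxicity or patient choice".
- **Section 7.12**: a patient who has to leave the combination because of a toxicity clearly due to one drug may stay on the other, provided that the local investigator and the Chief Investigator see continuing clinical benefit.

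Duration of trial treatment is a secondary outcome (sections 2.2 and 12.2.1.2). Best response and the transfusion, spleen and liver, and blood count outcomes are assessed around the end of cycles 3 and 6.

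**The concern.** The same two words lead to continuing treatment in one section and to stopping it in another. This is a multicentre trial, so two sites could see the same toxicity at the same dose level, take different actions, and each cite the protocol. One patient would go on at a reduced dose or on one drug; the other would be taken off treatment.

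Three things are at stake:

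- The description of treatment duration and exposure after cycle 1 would partly reflect how each site read the protocol as well as how tolerable the combination is.
- Routine adverse event collection runs until 28 days after the last treatment (section 8.1.3), so the choice also sets how long a patient contributes routine safety data.
- A site that uses the reduction allowed by 7.8.2 has departed from a mandatory instruction in 7.13, which creates avoidable questions about protocol compliance.

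**Working it through.** The protocol gives no figure on this point, so the check is a comparison of the text.

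1. **Is the trigger the same?** Yes. 7.8.2 and 7.13 both use unacceptable toxicity. The protocol neither defines nor grades it. It does specify other toxicity thresholds: DLTs are graded in section 2.2, and the paragraph on other non-haematological toxicities in 7.8.2 sets a grade for delaying cycles.

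2. **Do the actions differ?** Yes. 7.8.2 is permissive and leaves reduction of either drug, or both, to the local investigator. 7.13 is mandatory. It separates justifiable reasons for the investigator to stop from events after which the patient must stop, and places unacceptable toxicity in the second group.

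3. **Do the sections apply to different periods?** No. 7.8.2 starts when the DLT period is complete. The 7.13 list has no time limit, so both apply from cycle 2 onward.

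4. **Does a qualifier or cross-reference resolve it?** No. The 7.13 entry does not say that the toxicity must persist after reduction, and does not refer back to 7.8. The SAE entry in the same list is qualified: only an SAE that requires permanent discontinuation counts. The toxicity entry has no such limit.

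5. **Is the scope of stopping clear?** No. 7.8.2 says that one or both drugs may be concerned when it speaks of reduction or of discontinuation after long delays. 7.13 speaks of study treatment as a whole. Both the ruxolitinib-alone case in 7.8.2 and the single-drug continuation in 7.12 assume that a patient can stop one drug and keep the other. The 7.12 sentence cross-refers to 7.8.1, the DLT-period section, but its own wording is not confined to cycle 1.

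6. **Which outcomes can be affected?** The MTD uses DLTs in the first 28 days (section 12.2.1.1), and no dose modification is permitted in that cycle (section 7.8.1), so it does not depend on the later rules. Treatment duration and exposure after cycle 1 depend on them directly. An effect on response at cycles 3 and 6 is possible, but it is an inference and its size cannot be worked out from the protocol.

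**The case against.** The best defence is that the sections do different jobs: 7.8 covers dose modification and 7.13 covers discontinuation. Read in steps (reduce where that works, stop where toxicity remains unacceptable), both have effect. That reading is plausible and may be what was meant. However, no section states it, and the mandatory, unqualified wording of 7.13 does not follow from it. It is also fair to say that 7.8.2 leaves reduction to local discretion, so clearer terms would not remove all variation between sites. They would remove the variation that comes from contradictory instructions.

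The limits on the consequence also stand. Secondary outcomes are reported descriptively (section 12.3). Dose changes (7.8.2) and reasons for discontinuation (7.13) go on the CRF. Patients who stop are still followed. Differences in handling should therefore be visible in the data.

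A reader might infer more than the protocol supports, in three ways:

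- **That 7.12 is a second stopping rule for cycles 2 to 6.** The words "until loss of response or unacceptable toxicity" apply only to patients who continue because of benefit at the end of six cycles. For the earlier cycles, the relevant part of 7.12 is the sentence on continuing the other drug.
- **That the renal paragraph contradicts the delay limit.** It says "the current azacitidine cycle should be interrupted and the next cycle delayed until the eGFR resolves to" a stated level and does not repeat a time limit. But it sits under 7.8.2, whose general rule, beginning "If a patient experiences a delay of a new cycle for more than 4 weeks", has no renal exception. The two can be read together: recovery is the condition for resuming, and the general limit still applies.
- **That a number of affected patients can be given.** The protocol states no expected rate of unacceptable toxicity after cycle 1. Any count would rest on an assumed rate and on every such event being handled differently under the two sections.

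**Conclusion.** The inconsistency is real and lies mainly between one sentence in 7.8.2 and one entry in the 7.13 list. The single-drug provisions in 7.8.2 and 7.12 add to it, because the 7.13 entry does not accommodate them. A site acting under 7.8.2 or 7.12 breaches 7.13 as worded.

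The consequence is limited to treatment handling, exposure, and secondary and safety outcomes after cycle 1, with treatment duration the most directly exposed. The MTD is unaffected. The size of the effect cannot be derived from the protocol, and none is claimed.

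This conclusion assumes that the protocol text is what sites follow. Section 7.8.2 refers to the SPC for reductions, and that document was not available here. The 7.13 entry makes no reference to it, so the SPC would not by itself settle which section applies. A statistical analysis plan could not settle it either, since these are instructions to sites.

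**What to change.** Reconcile the unacceptable toxicity entry in section 7.13 with sections 7.8.2 and 7.12:

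- Use one defined term for toxicity that permits reduction or interruption and a different defined term for toxicity that requires stopping, and apply both consistently in all three sections.
- State in 7.13 whether stopping means the causative drug or both drugs, so that it fits the single-drug provisions in 7.8.2 and 7.12.
- Add a cross-reference from the 7.13 list to 7.8.

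Which toxicities fall under which term, and what action follows, is for the Chief Investigator and sponsor to decide. The cost is wording in the next protocol amendment. Sample size, dose-finding model and assessment schedule do not change.

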#### Cytopenias

Cytopenias will not be an indication for dose delay. MPN-BP is often associated with profound peripheral cytopenia (neutropenia, thrombocytopenia or anaemia). Patients who have these features at baseline or who develop these whilst on treatment may receive supportive care in the form of red cell or platelet transfusion or growth factor support at the local Investigator's discretion.

5-azacitidine and ruxolitinib are associated with cytopenias and bone marrow suppression and dose modifications are not scheduled for these events. In the event of severe bone marrow suppression or cytopenias following acquisition of a clinical response and not considered disease related, the CI must be informed to decide an appropriate course of action. Complete blood counts will be performed as per the above schedule, and at other time-points according to investigator discretion.

#### Renal toxicities

The kidney plays a significant role in the excretion of 5-azacitidine and ruxolitinib and the effects on renal function should be carefully monitored before the start of each cycle according to local protocols. If eGFR falls to between 30-39ml/min whilst the patient is receiving treatment with azacitidine,

bicarbonate levels should be measured at the time of serum biochemistry and patient should receive dose reductions according to SPC as applicable.

In the event of worsening kidney function (eGFR<30ml/min, grade 3 chronic kidney disease), the current azacitidine cycle should be interrupted and the next cycle delayed until the eGFR resolves to  $\geq$ 30ml/min.

#### Other non-haematological toxicities

Cycles may be delayed up to 4 weeks at the Investigator's discretion for non-haematological toxicities greater than grade 2 occurring after completion of cycle 1.

#### 7.9 Treatment Compliance – Interventional Component

Non-compliance is not expected for 5-azacitidine as patients must attend hospital to receive subcutaneous injections.

Ruxolitinib compliance will be measured in two ways. The local trial pharmacist will be responsible for maintaining and updating the drug accountability log in the PHAZAR pharmacy file. All unfinished bottles of ruxolitinib will be returned to the trial pharmacist who will count and document any unused medication. All IMPs can then be destroyed in accordance with local pharmacy practice and this will be documented on the drug destruction log in the hospital pharmacy file. In addition, patients will be issued with a Patient Diary which they will be asked to complete each day, recording the time that each dose was taken, and whether any doses were missed. The diary also includes a section where the patient can record any relevant information such as side effects suffered or reasons for missed doses. The completed diary will be collected by the centre at clinic visits and returned to the PHAZAR Study Office.

# 7.10 Supportive Treatment

#### **Interventional Component**

As ruxolitinib is associated with the development and reactivation of bacterial, fungal and viral infections, patients should be monitored for symptoms at protocol visits and use of antibiotic, antiviral and antifungal prophylaxis are advised as per local protocols. Special attention should be paid to the possibility of reactivation of tuberculosis and Herpes Zoster. Patients should be educated about the early symptoms of Herpes Zoster to enable them to notify the research team and receive treatment as soon as possible.

Patients may also receive treatment with G-CSF/GM-CSF and / or blood transfusions (red blood cells and platelets) as applicable. EPO and TPO are prohibited throughout the trial.

#### **Observational Component**

All supportive treatment permitted.

#### 7.11 Concomitant Medication

#### Interventional Component

The metabolism of Ruxolitinib is affected by CYP3A4 inducers and inhibitors. Strict attention to this detail is required.

#### CYP3A4 inhibitors:

#### Potent CYP3A4 inhibitors

Patients should not take any potent inhibitors of the CYP3A4 family of metabolising enzymes during the first cycle of treatment. Following completion of the DLT assessment period, potent CYP3A4 inhibitors are permitted but their use is strongly discouraged, however the dose of ruxolitinib may need to be adjusted.

Azole antifungals commonly used for fungal prophylaxis are potent inhibitors of the CYP3A4 pathway. Their use is therefore prohibited during the first cycle of treatment and discouraged from cycle 2

onwards. Alternatives permitted throughout the trial include Isavuconazole, Amphotericin B and Micafungin.

Isoniazid is also expected to affect ruxolitinib bioavailability. Therefore, alternatives should be discussed with the local infectious disease team if tuberculosis prophylaxis is needed. Active tuberculosis will mandate discontinuation of trial treatment.

When ruxolitinib is administered with strong CYP3A4 inhibitors or dual inhibitors of CYP2C9 and CYP3A4 enzymes (e.g. fluconazole), the dose of ruxolitinib should be reduced by approximately 50%, to be administered twice daily. Concomitant use of ruxolitinib with fluconazole doses greater than 200 mg daily should be avoided. More frequent monitoring (e.g. twice a week) of haematology parameters to detect cytopenias and of clinical signs and symptoms of ruxolitinib-related adverse drug reactions is recommended while strong CYP3A4 inhibitors or dual inhibitors of CYP2C9 and CYP3A4 enzymes and ruxolitinib are co-administered.

#### Mild or moderate CYP3A4 inhibitors

No dose adjustment is recommended when ruxolitinib is co-administered with mild or moderate CYP3A4 inhibitors. However, patients should be closely monitored for cytopenias when initiating therapy with a moderate CYP3A4 inhibitor.

#### CYP3A4 inducers:

Patients taking potent CYP3A4 inducers should be monitored proactively whilst on ruxolitinib and the dose titrated based on safety and efficacy. Where possible, an alternative therapy should be administered.

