# 4.2 Exclusion Criteria

#### Interventional Component:

- Any co-morbidity that could limit compliance with the trial or any other condition (including laboratory abnormalities) that in the Investigators opinion will affect the patient's participation in this trial
- New York Heart Association Class II, III, or IV congestive heart failure

- On-going cardiac dysrhythmias of grade 3, QTc prolongation >480 ms, or other factors that increase the risk of QT interval prolongation (e.g. heart failure, hypokalemia defined as serum potassium <3.0 mEq/L, family history of long QT interval syndrome)

- Erythropoietic agent within 28 days prior to registration
- Thrombopoietic agent within 14 days prior to registration
- Potent CYP3A4 inhibitor within 7 days prior to registration
- Experimental treatment within 14 days prior to registration
- Previous treatment for MPN-AP or MPN-BP, including stem cell transplant and low intensity AML chemotherapy
- Previously received 5-azacitidine. Ruxolitinib can be taken up until study entry at the pre-study dose. Hydroxycarbamide prescribed prior to study entry must be stopped before the first scheduled day of trial treatment
- Known contraindications to receiving 5-azacitidine or ruxolitinib
- Active infection ≥ grade 3 (CTCAE criteria) at trial entry
- Known HIV seropositivity
- Known to have active hepatitis A, B, or C
- Women who are pregnant or lactating. Patients of childbearing potential must have a negative pregnancy test prior to study entry
- Patients and partners of childbearing potential not willing to use effective contraception for the duration of the study treatment and for three months after the last dose

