#### Potent CYP3A4 inhibitors

Patients should not take any potent inhibitors of the CYP3A4 family of metabolizing enzymes during the first cycle of treatment. Beyond the first cycle such medication is discouraged but permitted, however the dose of ruxolitinib may need to be adjusted.

Potent inhibitors of the CYP3A4 include, but are not limited to:

- Clarithromycin
- Itraconazole
- Nefazodone
- Telithromycin
- Indinavir
- Ritonavir
- Cobicistat
- Troleandomycin
- Saquinavir
- Voriconazole

- Mibefradil
- Lopinavir
- Elvitegravir
- Posaconazole
- Nelfinavir
- Boceprevir
- Ketoconazole
- Telaprevir
- Fluconazole
- Isoniazid

Azole antifungals commonly used for fungal prophylaxis are potent inhibitors of the CYP3A4 pathway. Their use is therefore prohibited during the first cycle of treatment and discouraged from cycle 2 onwards. Alternatives permitted throughout the trial include Isavuconazole, Amphotericin B and Micafungin.

Isoniazid is also expected to affect ruxolitinib bioavailability. Therefore, alternatives should be discussed with the local infectious disease team if tuberculosis prophylaxis is needed. Active tuberculosis will mandate discontinuation of trial treatment.

When ruxolitinib is administered with strong CYP3A4 inhibitors or dual inhibitors of CYP2C9 and CYP3A4 enzymes (e.g. fluconazole), the dose of ruxolitinib should be reduced by approximately 50%, to be administered twice daily. Concomitant use of ruxolitinib with fluconazole doses greater than 200 mg daily should be avoided. More frequent monitoring (e.g. twice a week) of haematology parameters to detect cytopenias and of clinical signs and symptoms of ruxolitinib-related adverse drug reactions is recommended while strong CYP3A4 inhibitors or dual inhibitors of CYP2C9 and CYP3A4 enzymes and ruxolitinib are co-administered.

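### Potent CYP3A4 inducers have no washout and no cycle-1 ban, so a possibly under-exposed patient can count in the CRM at the allocated dose

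*Protocol*

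**What the plan says.** Section 7.11 of the protocol puts both drug classes on the same footing: "The metabolism of Ruxolitinib is affected by CYP3A4 inducers and inhibitors". The rules that follow differ.

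- **Potent inhibitors.** Section 4.2 excludes: "Potent CYP3A4 inhibitor within 7 days prior to registration". Section 7.11 adds: "Patients should not take any potent inhibitors of the CYP3A4 family of metabolising enzymes during the first cycle of treatment". The restriction is lifted only later: "Following completion of the DLT assessment period, potent CYP3A4 inhibitors are permitted but their use is strongly discouraged". Appendix 5 repeats the cycle-1 ban.
- **Potent inducers.** Section 4.2 has no criterion. Section 7.11 and Appendix 5 both say: "Patients taking potent CYP3A4 inducers should be monitored proactively whilst on ruxolitinib and the dose titrated based on safety and efficacy". Both add: "Where possible, an alternative therapy should be administered". Neither text refers to cycle 1. Appendix 5 lists examples, including carbamazepine, phenytoin and rifampicin.

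Section 7.8.1 fixes the dose in the DLT window: "No dose modifications will be permitted in the first cycle of treatment". Footnote 8 of the section 7.3 schedule agrees. Under section 12.1 the CRM uses all earlier data, including the first stage, at the assigned dose levels. Section 2.2 replaces patients who are not evaluable for DLT and gives unrelated death and withdrawal as examples. The list is open, and inducer use is not named.

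**The concern.** The MTD is the primary outcome, and it depends on cycle-1 DLTs credited to the allocated ruxolitinib dose. Co-medication that changes exposure in cycle 1 breaks the link between allocated and effective dose. The protocol guards against this for inhibitors, with a ban tied explicitly to the DLT window, but not for inducers.

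The one tool offered for inducers, titration, conflicts with the cycle-1 rule. If section 7.8.1 governs, which is the natural reading, the patient stays on the allocated dose and may be under-exposed. If the titration sentence governs, the dose taken is no longer the dose the model uses.

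An under-exposed patient is less likely to have a ruxolitinib-related DLT. A DLT-free result is then falsely reassuring and pushes the estimate towards a higher dose. What is at stake is bias in the dose estimate, not acute harm to the inducer user.

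**Working it through.** The protocol gives no figure to reproduce: no prevalence of inducer use, no exposure loss, no prior variance for the model parameter and no operating characteristics. The sizes below rest on stated assumptions.

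**From the protocol (section 12.1, with cohorts of 3-5 from section 3.1).** Target DLT rate 25%; maximum 34 patients; skeleton 0.05, 0.10, 0.15, 0.20, 0.25 for 5 to 25 mg bd; model x^exp(β); start at 10 mg; no skipping of levels; no escalation when the observed rate at the current dose exceeds 25%; early declaration once 12 patients are at the dose next recommended.

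**Assumed.** Share of users f = 1%, 2% or 5%; exposure loss r = 30%, 50% or 70%; true DLT risks of 0.05, 0.10, 0.15, 0.25, 0.40 and 0.50 at 0, 5, 10, 15, 20 and 25 mg, so the true MTD is 15 mg and the risk on azacitidine alone is 5%; normal prior on β with variance 1.34.

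**Step 1: how many users.** Expected number is 34f = 0.3, 0.7 and 1.7. The chance of at least one is 1 − (1 − f)^34 = 0.289, 0.497 and 0.825. The chance that a cohort of 3 contains one is 1 − (1 − f)^3 = 0.030, 0.059 and 0.143.

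**Step 2: a user's DLT risk at 15 mg.** The effective dose is 15(1 − r) = 10.5, 7.5 or 4.5 mg. By linear interpolation:
- 10.5 mg: 0.15 + 0.10 × 0.5/5 = 0.160
- 7.5 mg: 0.10 + 0.05 × 2.5/5 = 0.125
- 4.5 mg: 0.05 + 0.05 × 4.5/5 = 0.095

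**Step 3: one cohort of 3 at 15 mg.** With no user, P(no DLT) = 0.75³ = 0.422. With one user it is 0.75² × (1 − p) = 0.472, 0.492 or 0.509.

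**Step 4: whole trial.** Two-stage CRM, cohorts of 3, 20,000 simulated trials per setting with common random numbers (standard error of each difference at most 0.14 points), the 12-patient rule applied automatically, no toxicity stop. Probability of declaring an MTD that is too high:

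| Users | r = 30% | r = 50% | r = 70% |
|---|---|---|---|
| none | 20.4% | 20.4% | 20.4% |
| 1% | 20.8% | 21.0% | 21.1% |
| 2% | 21.1% | 21.5% | 21.8% |
| 5% | 22.2% | 23.1% | 23.8% |

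Across true MTDs of 10, 15 and 20 mg and cohorts of 3 or 5, the increase is 0.25-0.73 points at 1% use, 0.49-1.54 at 2% and 1.25-3.81 at 5%. A separately coded simulation of 10,000 trials (true MTD 15 mg, cohorts of 3) gave 20.7% with no users, 21.1-21.4% at 1%, 21.5-22.1% at 2% and 22.5-24.1% at 5%.

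**Step 5: one patient can change a decision.** This is a constructed case, not an expected effect. Take 0 of 5 DLTs at 10 mg, then 2 of 5 at 15 mg. The observed 40% exceeds 25%, so escalation is blocked. If one of those two DLTs is masked (1 of 5), the estimate at 25 mg is about 0.23 for prior standard deviations from 0.75 to 1.34. The model then points to 25 mg, and the trial escalates to 20 mg under the no-skip rule.

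**The case against.** - **Other text offers some protection.** Section 7.11 refers to Appendix 5 as the list of prohibited medication and asks for the sponsor to be told of prohibited therapies. Section 4.2 lets the investigator exclude for any condition thought to affect participation. Concomitant medication is recorded from baseline, and under section 13.4 the steering committee decides whether to follow each CRM recommendation. This lowers the risk without closing the gap: the inducer entry in Appendix 5 does not prohibit, the exclusion is generic, and co-medication is not named among the data the committee receives.
- **The titration conflict is mild.** Section 7.8.1 is explicit and would most likely prevail. That stands, but it leaves the user on the allocated dose, which is the problem described.
- **Evaluability rules usually belong in the SAP.** This largely stands. The finding does not depend on them.
- **The size rests on assumptions.** This stands. If the true MTD is 25 mg, the protocol's own prior guess, a dose above it cannot be chosen and the increase is zero. The assumed risk curve is steeper than Table 2. Countable DLTs are non-haematological and exclude infections, so how far lower exposure reduces them is uncertain. The simulation also leaves out the toxicity stop, committee override and interim review.
- **The asymmetry can be defended.** Inhibitors threaten over-exposure and patient safety; inducers do not. Barring inducers also costs some patients entry to a trial in a rare disease with few options. That is a fair reason to rate the point low, but it does not answer the bias in the primary outcome.

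**Conclusion.** The concern holds, as a minor point. The text leaves the DLT window open to potent inducers while closing it to potent inhibitors, and the mitigation offered cannot be used in cycle 1. The likely bias is towards too high an MTD. Its average size is small: under the assumed inputs, at most about 0.7 percentage points at 1% use, 1.5 at 2% and 3.8 at 5%, and zero if the top dose is the true MTD. Few users are likely, because known HIV is an exclusion, active tuberculosis ends treatment, and an alternative drug is preferred where possible. The protocol states neither the direction nor the amount of any exposure change, so lower exposure is itself an assumption.

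**What to change.** - **Section 4.2:** exclude use of potent CYP3A4 inducers before registration, with a washout period that the sponsor justifies.
- **Section 7.11 and Appendix 5:** prohibit potent inducers in cycle 1, and state that inducer-related titration applies only after the DLT assessment period.
- **Section 2.2 or the SAP:** set in advance how evaluability is decided for a patient who nevertheless takes a potent inducer in cycle 1. The schedule has no pharmacokinetic sampling, so base the rule on co-medication and dosing records, for example a number of days of use. Apply it identically whether or not a DLT occurred, and replace the patient if not evaluable. Any DLT is still reported and reviewed for safety.

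The cost is protocol wording. A few patients who need an inducer, such as some on anticonvulsants, could enter only the observational component, and an occasional patient would be replaced. No new data collection is needed, since concomitant medication is already recorded.
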